6.1 ANALYSIS OF PERCENTAGE OF TIME IN RANGE

The analysis of secondary endpoints that summarize the percentage of time in range (TIR) will follow the analysis set forth for the primary effectiveness endpoint of TIR 70-180 mg/dL, with the range value updated as appropriate.

6.2 ANALYSIS OF PERCENTAGE OF TIME IN HYBRID CLOSED-LOOP

The percentage of time in hybrid closed-loop will be calculated as:

$$100 \times \frac{\text{sum of gaps between consecutive CGM readings}}{\text{difference between the earliest and the latest CGM readings}} = \% \text{ time in HCL}$$

A gap is calculated as the difference in time (either minutes or seconds) between two consecutive CGM records as captured by the Horizon™ System. The gaps are then summed to obtain total time in HCL. As records are generally taken in about every 5 minutes, and to ensure that only confirmed HCL records are included, gaps greater than 7 minutes will be excluded from analysis. For the denominator, the chronologically earliest and latest CGM records during HCL as captured by the Horizon™ System will be used.

As opposed to the time in range endpoints, records with no glucose value in the Horizon™ System device output (such as due to an error or device deficiency during which the device does not record glucose readings) will be included in analysis. CGM records reported prior to the start of HCL or after the subject's discontinuation from HCL or during study pause will be excluded from analysis. This endpoint will also be reported separately for the manual and automated modes.

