**Figure 1: System components of the Omnipod Horizon™ System**

### 2.1.1. Omnipod Horizon™ Controller (App and Algorithm)

The Omnipod Horizon™ Controller is composed of two parts: the Horizon application (“app”) and the model predictive control (MPC) algorithm on the Pod. The MPC algorithm provides insulin micro-boluses once every 5 minutes based upon the predicted glucose over a 60-minute prediction horizon. Optimal post-prandial control will require the user to give meal boluses in the same manner as current pump therapy, but normal operation of the MPC algorithm will compensate for missed meal boluses and mitigate prolonged hyperglycemia. The MPC algorithm uses a control-to-target strategy that attempts to achieve and maintain a set target glucose value, thereby reducing the duration of prolonged hyperglycemia and hypoglycemia. The MPC algorithm resides on the Pod (Pump) component of the Omnipod Horizon™ System (similar to the DASH ACE pump cleared in K191679), as described further below).

The Omnipod Horizon™ app will be the primary user interface and will be used to start and stop a Pod, program basal and bolus calculator settings for Manual Mode as well as program settings specific for Automated Mode (hybrid closed-loop).

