#### Manual Mode

In Manual Mode, the Horizon™ System will function equivalently to the Omnipod® DASH System, which was first cleared under K180045, most recently under K191679.

This includes delivering insulin at programmed basal rates and bolus amounts with the option to set temporary basal profiles. The Omnipod Horizon™ Controller will also have the ability to function as a sensor augmented pump in Manual Mode, using sensor glucose data provided by the iCGM to populate the bolus calculator.

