3.3 SECONDARY OBJECTIVE AND ENDPOINTS

The secondary objective is to evaluate additional glycemic measures of effectiveness of the Omnipod Horizon™ Automated Glucose Control System. The secondary objective will be evaluated based on the following per subject endpoints *with* prespecified hypotheses:

- Glucose metrics from system CGM during the hybrid closed-loop phase for Phase 2 will be compared to Phase 1 overall:
 - Percentage of time in range > 180 mg/dL
 - Percentage of time in range < 70 mg/dL

Additional per subject endpoints *without* prespecified hypotheses used to evaluate the secondary objective include:

- A1C:
 - A1C after at least 8 weeks of continuous Phase 2 participation at the end of Phase 2 (Visit 13), 6 months (Visit 16) and the end of Phase 3 (Visit 19)
 - Change from baseline in A1C after at least 6 weeks of continuous Phase 2 participation, after at least 8 weeks of continuous Phase 2 participation, at the end of Phase 2 (Visit 13), 6 months (Visit 16) and the end of Phase 3 (Visit 19)
 - Proportion of subjects demonstrating an improvement from baseline in A1C after at least 6 weeks of continuous Phase 2 participation, after at least 8 weeks of continuous Phase 2 participation, at the end of Phase 2 (Visit 13), 6 months (Visit 16) and the end of Phase 3 (Visit 19)
- Glucose metrics from system CGM during the hybrid closed-loop phase for Phase 2 and Phase 3 will be compared to Phase 1 during the day, overnight, and overall:
 - Mean glucose
 - Percentage of time in range 70-180 mg/dL
 - Percentage of time in range 70-140 mg/dL
 - Percentage of time in range > 180 mg/dL
 - Percentage of time in range ≥ 250 mg/dL
 - Percentage of time in range ≥ 300 mg/dL
 - Percentage of time in range < 70 mg/dL
 - Percentage of time in range < 54 mg/dL
 - Standard deviation
 - Coefficient of variation
- Percentage of time in hybrid closed-loop as proportion of overall device usage time during Phase 2 and Phase 3
- Glucose management indicator (GMI) based on overall mean glucose during Phase 2 and Phase 3 will be compared to Phase 1
- Insulin requirements during Phase 2 and Phase 3 will be compared to Phase 1:

Statistical Analysis Plan

- Total daily insulin (TDI) (units, units/kg)
- Total daily basal insulin (units, units/kg)
- Total daily bolus insulin (units, units/kg)
- Change from baseline in BMI (kg/m^2) at end of Phase 2 and Phase 3

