7.6 EXPLORATORY ANALYSES

The following exploratory analyses will be considered. The analyses may be used for internal research purposes and/or scientific presentations and/or manuscripts and may not all be provided in a regulatory submission:

- Number of hypoglycemic and hyperglycemic events as measured by the system CGM during the hybrid closed-loop phase will be compared to the standard therapy phase
- Glucose metrics from the system CGM during the hybrid closed-loop phase stratified by device mode
- Change from baseline in A1C and BMI at the last follow-up visit, given at least 6 weeks of participation during Phase 2
- Change from baseline in A1C after at least 6 weeks of continuous Phase 2 participation, stratified by baseline A1C (e.g. A1C $\geq 7.5\%$, $\geq 9.0\%$)
- Proportion of subjects with A1C $<7.0\%$ at baseline and after at least 6 weeks of continuous Phase 2 participation; similar analyses using A1C cutoffs of $<7.5\%$, $<8.0\%$ and $<9.0\%$
- Proportion of subjects with change from baseline in A1C after at least 6 weeks of continuous Phase 2 participation of $>0.5\%$ and $>1.0\%$
- Proportion of subjects who either had an improvement from baseline of $>1.0\%$ in A1C or A1C $<7.0\%$ after at least 6 weeks of continuous Phase 2 participation
- Percentage of time the CGM was used during the HCL phase
- Number of meal and correction boluses
- Compare glycemic outcomes (e.g., TIR <70 mg/dL, TIR >180 mg/dL) by bolus frequency per day
- Compare glycemic outcomes (e.g., TIR <70 mg/dL, TIR >180 mg/dL) by use of CGM informed bolus calculator (i.e., days with CGM informed bolus calculator used at least once and days without CGM informed bolus calculator use)
- Post-prandial glucose response including time to peak glucose, peak glucose concentration, peak glucose excursion, to meals with bolus (challenge days 1 and 3) vs no bolus (challenge days 2 and 4)
- Glycemic outcomes and other measures based on evaluable subjects (i.e., those subjects with at least 8 weeks of data during the HCL phase)

Statistical Analysis Plan

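### The percentage of time in hybrid closed-loop in SAP 6.2 does not depend on device mode, so it measures CGM record continuity and not Automated Mode use

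*SAP*

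**What the plan says.** SAP 3.3 lists the endpoint as "Percentage of time in hybrid closed-loop as proportion of overall device usage time during Phase 2 and Phase 3"; SAP 6 and Protocol 6.3.1 and 13.2.4 have it too. It is a secondary endpoint without a prespecified hypothesis.

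SAP 6.2 gives the calculation.

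- **Numerator.** A gap is the time between two consecutive CGM records captured by the Horizon System. "The gaps are then summed to obtain total time in HCL".
- **Filter.** The reason given for the gap limit is that "to ensure that only confirmed HCL records are included, gaps greater than 7 minutes will be excluded from analysis".
- **Denominator.** It is the time between two records: "the chronologically earliest and latest CGM records during HCL as captured by the Horizon™ System will be used".
- **Other inclusions and exclusions.** Unlike the time-in-range endpoints, this one keeps "records with no glucose value in the Horizon™ System device output". It drops records from before the start of HCL, after discontinuation, or during a study pause.
- **Mode.** The last sentence of SAP 6.2 adds that the endpoint will also be shown separately for manual and automated modes.

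Three other places bear on the meaning. Protocol 2.1.1 gives hybrid closed-loop in brackets as another name for Automated Mode, and the per-protocol definitions (Protocol 13.4.3, SAP 7.1.3) pair it with automated as against manual. The Manual Mode paragraph of the protocol says the controller can also "function as a sensor augmented pump in Manual Mode, using sensor glucose data provided by the iCGM". SAP 2.8 refers to Horizon CGM readings taken in Manual Mode and counts Phase 2 participation in either mode.

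**The concern.** A share of device usage is informative only if some usage is not hybrid closed-loop. On the documents' own terms, the part that is not is Manual Mode. The SAP 6.2 numerator has no condition on mode, and Manual Mode also yields CGM records, so Manual intervals enter the sum labelled as time in HCL. The 7-minute rule cannot do the job assigned to it: it detects missing records, but an unbroken run of Manual Mode records passes just as an Automated run does.

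The denominator also differs from the endpoint's name. Elapsed time between two records is not usage time, and dropping pause records does not by itself take the pause out of the interval between the first and last record.

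The endpoint shows how much of the exposure was to the automated function, and a reader would use it to interpret the time-in-range and A1C results. Calculated as written, it cannot show that. The SAP overrides the protocol where they differ (SAP 1, Protocol 13.11), so the formula in SAP 6.2 is the one that will be programmed.

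**Working it through.** The documents state no value for this endpoint, no Manual Mode share and no rate of CGM loss, so there is no figure to reproduce. The shares below are assumptions.

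**Notation**, as fractions of elapsed time with no pause: c = time covered by gaps of 7 minutes or less; m = the part of c spent in Manual Mode; c − m = captured Automated time. Usage time is taken as captured Automated plus captured Manual time, which equals c.

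**Formulas**

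- SAP 6.2 headline: c. It does not contain m.
- Automated time over the same span: c − m. The headline exceeds this by m.
- Automated time over usage time: (c − m)/c = 1 − m/c. The headline minus this is m/c − (1 − c), which is positive when m > c(1 − c).

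The break-even Manual share is 0.95 × 0.05 = 4.75% of elapsed time at 95% capture, and 0.90 × 0.10 = 9% at 90% capture. This is close to the share lost to long gaps (5% and 10%).

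| c | m | SAP 6.2 | Automated / span | Automated / usage | SAP 6.2 minus Automated / usage |
|---|---|---|---|---|---|
| 95% | 0% | 95% | 95% | 95/95 = 100% | −5.0 |
| 95% | 5% | 95% | 90% | 90/95 = 94.7% | +0.3 |
| 95% | 10% | 95% | 85% | 85/95 = 89.5% | +5.5 |
| 95% | 25% | 95% | 70% | 70/95 = 73.7% | +21.3 |
| 95% | 30% | 95% | 65% | 65/95 = 68.4% | +26.6 |
| 90% | 5% | 90% | 85% | 85/90 = 94.4% | −4.4 |

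At the extreme, a subject in Manual Mode throughout with 95% capture still scores 95%; the Automated share is zero.

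**Literal application to simulated records.** The formula was applied to 5-minute records over 91 days, with loss in random two-hour blocks and Manual Mode in whole days (0, 5, 9, 18 or 27 of 91). Here usage time includes time with lost records.

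- At 5% loss, SAP 6.2 gives 94.8% for all five Manual shares. Automated over span gives 94.8, 89.4, 85.4, 75.9 and 66.7%. Automated over usage gives 100, 94.5, 90.1, 80.2 and 70.3%.
- At 15% loss, SAP 6.2 gives about 84.4%. That is below Automated over usage for 5 and 9 Manual days (94.5%, 90.1%) and above it for 18 and 27 (80.2%, 70.3%).

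**Study pause.** SAP 2.8 expects most subjects to have Phase 2 data on both sides of a pause. The example in Protocol 9.11 pauses on 28 February 2020 (day 28) and resumes on 1 May 2020 (day 29), so 1 + 31 + 30 = 62 days lie between. If the span runs literally from first to last record, a subject always in Automated Mode with no lost records reaches at most 94/(94 + 62) = 60.3% at the Visit 13 target of day 94, or 91/(91 + 62) = 59.5% for 13 weeks.

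**The by-mode figures.** SAP 6.2 does not say what they are divided by. If each mode uses the span of its own records, one unbroken Manual day in 13 weeks scores about 100% Manual. Divided by 91 days, it scores 1/91 = 1.1%. The two readings are not interchangeable.

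**The case against.** The best defence is that SAP 6.2 already plans a split by mode. A subject who keeps leaving Automated Mode could be seen there, and the pooled row would only be a first line. The SAP also uses HCL for the phase (SAP 2.3, and in SAP 6.2 itself for its start and discontinuation). On that reading, total time in HCL means captured time on the system during the phase, and the fault is largely one of labelling. The consequences are limited too: SAP 6.6 says these analyses will not support clinical claims.

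Part of this stands. A reader might infer from SAP 6.2 more than the documents support:

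- *That every CGM interval is counted.* Gaps over 7 minutes are excluded, as are records from a pause and from outside the phase.
- *That this is the only measure of automated use.* A report by mode is planned, the data portal shows time spent in each mode (Protocol 3), and glucose metrics by mode are listed as exploratory.
- *That the figure always overstates closed-loop use, by exactly the Manual share.* That holds only against elapsed time. Against usage time the error in the 25% example is 21.3 points, and with little Manual Mode or much CGM loss the figure is too low. A span that includes the pause lowers it further.
- *That it duplicates the exploratory item* "Percentage of time the CGM was used during the HCL phase". It looks close, but SAP 7.6 gives no formula for that item.

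The defence does not remove the defect. The word *also* in the by-mode sentence leaves the pooled figure as the endpoint, and the by-mode figures have no stated denominator. Reading HCL as the phase makes the calculation consistent with itself, but it is then no longer the share of device usage that SAP 3.3 names.

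**Conclusion.** The rule is wrong as written. The headline in SAP 6.2 does not respond to device mode, and its denominator is not device usage time, so it cannot measure the endpoint named in SAP 3.3.

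The direction and size of the error depend on quantities the documents do not give. For assumed Manual shares of 5 to 30% of elapsed time at 95% capture, the figure is 5 to 30 points above Automated time over the same span, and 0.3 to 26.6 points above Automated time over usage time. With no Manual Mode at 95% capture, or 5% Manual at 90% capture, it is 5.0 and 4.4 points below the latter. The cap of about 60% applies only if the pause is left in the denominator; the SAP excludes pause records but does not say whether pause time is subtracted.

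The endpoint is secondary and carries no hypothesis. Alpha, power, sample size and the study-success criterion do not depend on it, and neither do the A1C and time-in-range calculations, since SAP 2.8 counts Phase 2 participation in either mode.

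**What to change.** In SAP 6.2:

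1. Define the percentage of time in hybrid closed-loop as the sum of gaps of 7 minutes or less flagged Automated Mode, divided by total device usage time (Automated plus Manual) with study-pause time excluded.
2. State how usage time is measured (for example, as gaps of 7 minutes or less in either mode) and which mode a gap belongs to when the mode changes between its two records.
3. Name this figure as the endpoint, and give the Manual figure the same denominator.
4. Report the all-mode figure separately as system/CGM use. It is nearer to what the 80% system-use rule of the per-protocol set (SAP 7.1.3) requires.
5. Remove the statement that the 7-minute rule secures confirmed HCL records, or restate it as a rule on missing records.

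The cost is a small change in wording and programming. The split already planned implies that mode is recorded. The headline figure may become less favourable.

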#### **5.2 Study Design**

This is a single-arm, multi-center, prospective clinical study. A total of up to 240 subjects aged 6-70 years with type 1 diabetes will be enrolled in the study in order to obtain a minimum of 200 evaluable subjects, 100 evaluable subjects in each age cohort (Table 1: Cohorts). Subjects will be considered evaluable if they have at least 8 weeks of data during Phase 2.

[figure not shown]
Subjects will be enrolled across 12-20 clinical study sites. Subjects who have previously participated during the feasibility studies may be enrolled in the pivotal study and will be assigned a new subject identification number. Subjects who have participated in the prepivotal study may participate in the pivotal study if it has been deemed safe for their continuation in the study and will retain their prepivotal subject identification number.

The study schedule consists of the following three phases:

- 1) 14-day outpatient standard therapy phase (Phase 1)
- 2) 13-week outpatient hybrid closed-loop phase (Phase 2)
  - A subset of subjects will participate in 5-days of supervised challenges
  - Phase 2 excludes periods due to a study pause
- 3) 12-month hybrid closed-loop extension phase (Phase 3)

Note: Subjects having completed the prepivotal study may participate in this pivotal study and begin at Phase 2 since Phase 1 was completed as part of the prepivotal study and is not required to be repeated.

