1 PURPOSE

The purpose of this Statistical Analysis Plan (SAP) is to describe the statistical methodology that will be used to confirm the safety and effectiveness of the Omnipod Horizon™ Automated Glucose Control System in patients with type 1 diabetes. Should there be any discrepancy between the pivotal study protocol and this SAP, the content of the SAP shall prevail.

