2.8 DEFINITION OF PHASE 2 AND PHASE 2 PARTICIPATION

For the majority of subjects, Phase 2 of hybrid closed-loop data will include both data collected prior to a study pause and data collected after the recommencement. Unless otherwise specified, any data that may have been collected during a study pause (including but not limited to CGM readings from the Horizon system while in Manual Mode), will be excluded from analyses.

Continuous Phase 2 participation refers to the length of time on the Horizon system (either in Automated or Manual Modes) and is calculated as:

- Commencement of Phase 2 until a study pause (for subjects who started Phase 2 prior to a study pause)
- Recommencement until discontinuation from the Horizon system or end of Phase 2 (for subjects who started Phase 2 prior to a study pause)
- Commencement of Phase 2 until discontinuation from the Horizon system or end of Phase 2 (for subjects who started Phase 2 after a study pause)

If a subject has ≥ 6 weeks on the Horizon system during Phase 2 prior to a study pause and ≥ 6 weeks on the Horizon system during Phase 2 after the recommencement, the longer interval will be used for analysis of A1C. Specifically, the A1C associated with the longer interval, if available, will be used for the analysis of the A1C endpoints.

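### SAP 6.2 leaves the study pause in the denominator of percentage of time in hybrid closed-loop, so the Phase 2 value is scaled down by T/(T+P) for subjects with data on both sides of a pause

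*SAP*

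**What the plan says.** SAP 6.2 defines the endpoint as a ratio.

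- **Numerator:** the sum of time gaps between consecutive CGM records, where "gaps greater than 7 minutes will be excluded from analysis".
- **Denominator:** the time between "the chronologically earliest and latest CGM records during HCL" as captured by the system.
- **Pause rule:** CGM records before the start of HCL, after discontinuation "or during study pause will be excluded from analysis".
- **Modes:** the same endpoint is also to be reported separately for Manual and Automated Mode.

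Other sections say what the figure should represent. SAP 3.3 names the endpoint "Percentage of time in hybrid closed-loop as proportion of overall device usage time during Phase 2 and Phase 3". Protocol 5.2 states that "Phase 2 excludes periods due to a study pause". SAP 2.8 excludes data collected during a pause and says that for most subjects Phase 2 "data will include both data collected prior to a study pause and data collected after the recommencement". It also provides "for subjects who started Phase 2 after a study pause", who have no pause inside the phase.

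During a pause, subjects could use the system in Manual Mode or return to their own system (Protocol 9.10). Up to 42 subjects delay recommencement to take part in a parallel study (Protocol 9.11).

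**The concern.** The pause rule in SAP 6.2 acts on records, whereas the denominator depends only on the two end records. Deleting records in the middle moves neither end, so the calendar time of the pause is still counted as time in which the subject could have been in HCL. The numerator gets no credit for that time.

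The reported Phase 2 percentage would therefore depend on how long the subject was paused as well as on how the system was used. It would understate use for most subjects. It would also mix subjects on different scales in one summary: those paused in mid-phase, those who started afterwards (P = 0), and those whose return was deferred. A reader would take a low value as poor system use or lost connectivity when it may only reflect a long pause.

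**Working it through.** **Inputs**

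- T, Phase 2 time outside the pause: 91 days (13 weeks, SAP 2.3) or 94 days (Visit 13 is scheduled on Study Day 94 ± 3, Protocol 9.9).
- P, pause length: no study-wide figure is given. The only dated illustration is in Protocol 9.11, where a subject pauses on 28 February 2020 after 28 days of participation and resumes on 1 May 2020 as Day 29. The days between are 29 February (1), March (31) and April (30), so P = 1 + 31 + 30 = 62 days. All other values of P below are assumptions.

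The dates in that example are consistent: Day 38 falls on 10 May with a window of 7 to 13 May, as the protocol says. Neither document states an expected value for this endpoint, so there is no figure of the plan's own to reproduce.

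**Formula.** Let N be the summed gaps of 7 minutes or less. The interval from the last pre-pause record to the first record after recommencement is one gap of length P. It exceeds 7 minutes, so it adds nothing to N. This is so whether the subject used Manual Mode during the pause (records deleted) or their own system (no such records).

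- SAP 6.2 as written: 100 × N / (T + P)
- Pause left out of Phase 2: 100 × N / T
- Ratio of the two: T / (T + P)

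**Score of a subject with complete records (true value 100%)**

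| Pause P | T = 94 days | T = 91 days |
|---|---|---|
| 7 days (assumed) | 94/101 = 93.1% | 91/98 = 92.9% |
| 14 days (assumed) | 94/108 = 87.0% | 91/105 = 86.7% |
| 28 days (assumed) | 94/122 = 77.0% | 91/119 = 76.5% |
| 56 days (assumed) | 94/150 = 62.7% | 91/147 = 61.9% |
| 62 days (Protocol 9.11 example) | 94/156 = 60.3% | 91/153 = 59.5% |

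The same factor applies at any level of use. With T = 91, a true 95% would be reported as 95 × 91/119 = 72.6% for a 28-day pause and 95 × 91/153 = 56.5% for 62 days.

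**Ranking.** With T = 94, a subject with 80% use and no pause scores 80.0%. A subject with 100% use and a 28-day pause scores 77.0%. The order of the two is reversed.

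**Check on simulated records.** SAP 6.2 was applied literally to five-minute records with 28 days before the pause, a 62-day pause, and the rest of Phase 2 after it.

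- Complete records, T = 94: 60.26% as written, 100.0% with the pause interval removed from the denominator.
- 3% of records missing at random, T = 94: 56.64% as written, 93.99% with the pause removed.
- Ratio: 0.6026 in both cases, equal to 94/156. With T = 91 it was 0.5948, equal to 91/153.

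**A repair that does not work.** Dropping every gap over 7 minutes from the denominator as well makes numerator and denominator the same sum. Every subject's overall figure would be 100%, even with about 20% of record hours deleted.

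**The case against.** The strongest reply is that the intent is plain. SAP 6.2 mentions the pause, SAP 2.8 excludes pause data and counts participation in separate intervals, and a sensible programmer could compute by segment. The intent is indeed clear, and the documents cannot show what will be programmed. But no sentence in either document subtracts pause time. Reading the end records as confined to HCL does not help, because both lie in HCL and their difference still spans the pause. A programmer who computes by segment departs from the written formula, and Protocol 13.11 requires departures from the final SAP to be described in the study report.

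Several narrower objections stand.

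- The SAP's precedence over the protocol ("Should there be any discrepancy between the pivotal study protocol and this SAP, the content of the SAP shall prevail") adds little, since the intent to exclude the pause is in the SAP too. The SAP has to be reconciled with itself.
- A segment-based denominator is still elapsed time and still counts ordinary gaps over 7 minutes, so it is not strictly device usage time. The firmer conflict is with the definition of Phase 2.
- Using total recorded time as a common denominator would give informative Manual and Automated shares, although the overall figure would remain 100%.
- The 62 days come from a visit-scheduling example, not from observed data. Protocol 9.10 plans visits about every 4 weeks until the study resumes, which suggests that long pauses were foreseen. That interval runs from the last visit, however, so it does not fix a pause length.
- The endpoint has no hypothesis, and SAP 6.6 says these results will not support clinical claims.

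These points limit the consequence. They do not change the result of the formula.

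**Conclusion.** The point holds. As written, SAP 6.2 multiplies the Phase 2 percentage of time in HCL by T/(T+P) for every subject with records on both sides of a pause, which SAP 2.8 describes as the majority. The factor is exact when P is the interval between the last pre-pause and first post-recommencement records. Its size depends on pause lengths that the documents do not give: at T = 94 days, about 0.93 for a 7-day pause, 0.77 for 28 days and 0.60 for the 62-day example. Subjects who started after the pause are unaffected.

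The damage is confined to one descriptive secondary endpoint and its Manual and Automated breakdowns. The primary tests, the two secondary endpoints with hypotheses, type I error and the study success criterion are untouched. It should still be corrected, because it is a named Phase 2 endpoint and SAP 2.3 says that Phase 2 results are intended for the marketing submission.

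**What to change.** In SAP 6.2, define the Phase 2 denominator for a paused subject as:

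(last pre-pause record − first Phase 2 record) + (last Phase 2 record − first record after recommencement)

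For subjects with no pause, keep last minus first Phase 2 record. Use the same total as the denominator for the Manual and Automated Mode figures. For completeness, state that Phase 3 is calculated from its own first and last records.

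The cost is two or three sentences in the SAP and a few lines of programming. No new data are needed, because the visit rules in Protocol 9.11 already depend on each subject's pause and recommencement dates. In the 62-day example, the change restores a subject with complete records from 60.3% to 100%.
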